1.0 Research Design

1.1 Purpose/Specific Aims

A. Objectives

This study will examine the feasibility, acceptability, and utility of neuroimaging technique to evaluate pre-exposure prophylaxis (PrEP) promotion messages for men who have sex with men (MSM) at risk of HIV in Baltimore, MD. The **specific aim** is:

Evaluate the effectiveness of PrEP promotion messages developed via a crowdsourcing open contest¹ by assessing neural bases of persuasion.

B. Hypotheses / Research Question(s)

This is an experimental study using neuroimaging technique to assess the persuasiveness of messages developed by a crowdsourcing open contest approach the study team conducted previously.

We hypothesize that, compared with participants viewing messages developed by a social marketing approach:

- H1. Participants viewing top messages developed via open contests will show higher brain activation in the Medial Prefrontal Cortex (MPFC) regions.
- H2. A greater proportion of participants viewing top messages developed via open contests will report increased willingness and behavioral intention to take PrEP.
- H3. A greater proportion of participants viewing top messages developed via open contests will report taking PrEP action and initiation during 30-day follow up.
- H4. Brain activation in the MPFC regions is significantly more correlated with PrEP action and initiation than self-reported message effectiveness.

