1.3 Research Design and Methods

This study is a randomized control trial (RCT). A total of 60 participants will be recruited and enrolled into this RCT where half of them will view PrEP promotion messages developed via a crowdsourcing open contact¹ and half of them will view PrEP promotion messages developed via social marketing.

A. Research Procedures

This study will be conducted as follows:

- Screening will be conducted in person after an oral consent. Once an individual is screened eligible, he will provide an informed consent and complete a baseline survey. A 2nd in-person visit will be scheduled, roughly a week after completing the baseline survey.
- During the in-person visit, participants will be randomized to one of two conditions: a) viewing top three messages developed by an open contest implemented in Baltimore, or b) viewing PrEP campaign messages that were developed with a traditional social marketing approach.
- After the randomization, a research assistant will take the participant to a private interview room. The research assistant will measure and fit the participant's head for the fNIRS headband, which is connected to a NIRSport. NIRSport is a portable fNIRS device to measure the neural response as participants view various messages on a computer screen with audio computer assistance. Similar to functional magnetic resonance imaging (fMRI), fNIRS is a non-invasive neuroimaging technique to measure key brain regions associated with influence and persuasion. Unlike fMRI, fNIRS only collects data ~3 cm into the cortex, yet the advantages of fNIRS are that it is small, portable, quiet, and does not require being still in a narrow tube. Employing harmless light sources, fNIRS is safe for studies with infants and adults as well. fNIRS involves wearing a lightweight cap from which LED lights are directed into the brain. The LED light emerges from the brain in predictable patterns and the way in which active brain tissue absorbs light allows us to reconstruct fMRI type images of the activity in the cortical surface. fNIRS have been widely used in social neuroscience research.
- Participants in each group will view multiple messages on a computer screen while brain activity is recorded.
- After completing all messages, participants will answer questions on perceived effectiveness of the messages, self-efficacy, and willingness and behavioral intention to use PrEP. Semi-structured questions on the acceptability of fNIRS will also be asked.

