1.5 Sample Size Justification

We aim to recruit 60 participants. In a recent systematic review of 20 studies that examined persuasive processing and outcomes of the health messages using neurocognitive measures,⁹ the sample size ranged from 14 to 91.⁵ Our primary goal for conducting this experimental study is to examine any preliminary evidence for the efficacy of an open contest approach to develop effective PrEP promotion messages. Effect-size estimates determined through this study will be essential in the design of a larger and fully powered efficacy study that tests intervention effects on PrEP uptake.

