Behavioral Intention: We will assess behavioral intentions to actually begin PrEP based on a real-world situation. To do this, participants will be asked, “PrEP is currently available with a prescription from your doctor and research has shown that a majority of insurance companies cover most or all of the costs of PrEP. Do you plan to begin PrEP?” Response options range from “Yes, I will definitely begin taking PrEP” to “No, I definitely will not begin taking PrEP.”

PrEP action and initiation: Items include “Have you spoken with a provider about PrEP during the past 30 days?” and “Have you started taking PrEP during the past 30 days?”

Message-related measures:

All questions will be asked after participants finish reviewing all messages during the in-person visit.

Perceived effectiveness: Participants will be asked, on a 4-point Likert scale ranging from strongly disagree to strongly agree, to rate their agreement that the message is believable, new, unconvincing, important to them, helps them feel confident about using PrEP, would help their friends use PrEP, put thoughts in their mind about using PrEP.

Baseline survey

Socioeconomic status: We will collect data on age, highest level of education attained, housing, employment history, health insurance status, access to health care, sources and amount of personal and household income,

Sexual identity: We will use a question from our previous study which asks participants to choose from heterosexual/straight, bisexual, homosexual/gay/same-gender loving, or not sure/questioning.

Sexual history: number of sex partners, sex of the partners, condom use in the past 90 days

Social media use: Types of social media sites used for socializing, seeking sex partners, and seeking health-related information.

HIV testing history

- **Ethnographic Studies, Interviews, Or Observation:**

N/A

- **Subject Identifiers:**

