4.3 Number of Subjects

A. Total Number of Subjects

We expected to screen 100 individuals. Seventy will be eligible and consent for participation. We need 60 individuals to complete the study.

B. Total Number of Subjects If Multicenter Study

N/A

C. Feasibility

[name] has a long history of working with local community partners to recruit study participants.

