Next, we will conduct primary inferential analyses to compare a) the level of neural activity in MPFC, b) increase in willingness and behavioral intention to take PrEP between baseline and 30-day follow up (yes/no), and c) PrEP action and initiation at 30-day follow up (yes/no) among participants in the three conditions. fNIRS detects the ratio of oxygenated (O₂HB) to deoxygenated (HHB) hemoglobin based on their optical properties, with higher ratios indicating greater neural activity. By modulating light at different wavelengths, emitting the light on the skin-exposed areas of the cranium, and detecting that light, fNIRS measures the blood oxygenation level dependent signal (BOLD) similar to fMRI. Because the photons reflected from neural tissue follow a reliable 'banana-shaped' path, photodetectors can be used to measure this on the scalp. By measuring the amount of absorbed light directed at the neural tissue, we can measure the amount of O₂HB and HHB present in a region of the brain at a given time and draw inferences about the level of neural activity. The level of brain activation for the top message condition compared to references will be evaluated using pairwise comparison. For the binary outcome measures, increase in willingness and behavioral intention to take PrEP and PrEP action and initiation, we will first compare proportions by conditions separately for each measurement period using standard bivariate analytic techniques such as Spearman rank-order correlations, odds ratios, and Fisher's exact test. Then we will employ generalized linear mixed

models (GLMM) to evaluate the effectiveness of top messages developed via open contest. GLMM permits us to measure the fixed effect of the top messages developed via open contest on neural activity, willingness and behavioral intention to take PrEP, and PrEP action and initiation, while allowing a random effect that accounts for within-person correlation. Given the binary nature of two primary outcomes, we will specify a logit link function for our GLMM models. Comparisons of characteristics of participants who are lost to follow-up to those who are evaluated will be conducted to assess for systematic patterns that could influence results.

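### PrEP initiation (part of H3): the odds ratio and logit model have no finite estimate if one arm has no starters, and section 6.1 gives no fallback

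*Combined protocol and SAP*

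**What the plan says.** H3 in section 1.1 predicts: "A greater proportion of participants viewing top messages developed via open contests will report taking PrEP action and initiation during 30-day follow up". Section 1.9 measures this with two items. The action item is "Have you spoken with a provider about PrEP during the past 30 days" and the initiation item is "Have you started taking PrEP during the past 30 days". Both are asked only at the 30-day follow-up, so each man contributes one answer per item. Men who have ever taken PrEP are not eligible (section 4.1), so every starter is a first-time user.

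On size, section 1.3 states "A total of 60 participants will be recruited and enrolled into this RCT", split equally between the arms. Section 4.3 expects 70 eligible and consenting men and adds "We need 60 individuals to complete the study". That is about 30 analysed per arm.

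On analysis, section 6.1 first compares proportions by condition, listing Spearman correlations, odds ratios and Fisher's exact test. It then evaluates effectiveness with a generalised linear mixed model: "Given the binary nature of two primary outcomes, we will specify a logit link function for our GLMM models". Baseline variables found to be imbalanced are added to the models. The section does not say which analysis decides H3, whether the model test is Wald or likelihood ratio, or what happens when a cell is zero.

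On purpose, section 1.5 says: "Effect-size estimates determined through this study will be essential in the design of a larger and fully powered efficacy study". That later study is to test effects on PrEP uptake.

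**The concern.** The odds ratio and the logit coefficient are the between-arm effect measures that 6.1 names for initiation. Both are undefined as finite numbers when one arm has no events (quasi-complete separation). The fitted log odds ratio drifts to wherever the software stops, its standard error becomes enormous, and the Wald statistic goes to zero however many starters the other arm has. The person random effect is not the cause: an ordinary logistic model for one record per man fails in the same way. Adding imbalanced covariates makes separation more likely.

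The stake is the estimate. The study presents itself as the source of effect sizes for a trial on uptake, and for the uptake item itself the planned model may have none to give. With the test statistic left open, the same table can also be reported with very different p-values.

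**Working it through.** **Inputs.** From the documents: 60 men, 1:1, so n = 30 per arm (sections 1.3 and 4.3); one yes/no answer per man (section 1.9). Not in the documents: the 30-day initiation rate, any effect size, and any power. I therefore show a range of rates. Alpha of 0.05 is stated only for the baseline comparisons; two-sided 0.05 for H3 is my assumption. The total of 60 is supported only by the range of sample sizes in a systematic review (14 to 91), so there is no planned figure to reproduce.

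**Step 1: how often a given arm is empty.** P(no starters) = (1 − p)^30.

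| True rate in the arm | P(no starters among 30) |
|---|---|
| 2% | 55% |
| 3% | 40% |
| 5% | 0.95^30 = 21% |
| 7% | 11% |
| 10% | 0.90^30 = 4.2% |
| 15% | 0.8% |
| 20% | 0.1% |

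At a 5% rate the figure is 28% with 25 per arm and 17% with 35 per arm.

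**Step 2: at least one empty arm.** P = 1 − [1 − (1 − p_c)^30][1 − (1 − p_t)^30]. This gives 64% at 3% v 3%, 43% at 3% v 10%, 38% at 5% v 5%, 22% at 5% v 20%, 8% at 10% v 10% and 4% at 10% v 20%.

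**Step 3: what each method returns when one arm is empty.** The maximum-likelihood logit was fitted with no random effect, as there is one record per man.

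| Table | Wald p | Likelihood-ratio p | Fisher p | Firth odds ratio (penalised LR p) |
|---|---|---|---|---|
| 3/30 v 0/30 | 0.999 | 0.038 | 0.24 | 7.8 (0.10) |
| 5/30 v 0/30 | 0.999 | 0.007 | 0.052 | 13.2 (0.021) |
| 6/30 v 0/30 | 0.999 | 0.003 | 0.024 | 16.2 (0.009) |
| 7/30 v 0/30 | 0.999 | 0.001 | 0.0105 | 19.5 (0.004) |
| 10/30 v 0/30 | 0.999 | <0.001 | 0.0008 | 31.2 (<0.001) |

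For 7/30 v 0/30 the software's log odds ratio is 22.4 with standard error about 14,508, so z = 22.4/14,508 = 0.0015 and p = 0.999. Fisher's two-sided p is 2 × C(30,7)/C(60,7) = 0.0105. With no covariates, the Firth odds ratio equals adding 0.5 to each cell: (7.5 × 30.5)/(23.5 × 0.5) = 19.5.

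**Step 4: the difference in proportions for the same table.** 7/30 − 0/30 = 23.3 points. The Wilson limits are 0.118 to 0.409 for 7/30 and 0 to 0.114 for 0/30. Newcombe's lower limit is 0.233 − √[(0.233 − 0.118)² + 0.114²] = 0.071. The upper limit is 0.233 + (0.409 − 0.233) = 0.409. The interval is 7.1 to 40.9 points.

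**Step 5: how often an empty arm coincides with a Fisher-significant result.** Step 3 shows that this needs at least 6 v 0. The probability is 2.9% at 3% v 10%, 12% at 5% v 20%, 17% at 5% v 25% and 2.4% at 10% v 20%. Among Fisher-significant tables, 51% have an empty arm at 5% v 20%, and about a quarter do at 10% v 20%.

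**The case against.** A reader might infer four stronger things from these results. The documents do not support any of them.

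- *That a strong effect would be missed.* Section 6.1 names Fisher's exact test alongside odds ratios, and that test is valid with a zero cell. Comparing proportions by condition also shows the raw difference, and the listed Spearman correlation stays finite. So a valid test and a descriptive contrast remain. What remains missing is an interval for the difference and a finite odds ratio or adjusted estimate.
- *That the planned model test gives p near 1.* This is a property of the Wald test, and the plan names no test. A likelihood-ratio test gives 0.001 for 7/30 v 0/30. It is not a cure, though: it is liberal at these counts (0.038 for 3/30 v 0/30, where Fisher gives 0.24) and leaves the estimate infinite.
- *That initiation is known to be rare.* No rate is given. The men are selected as PrEP candidates and both arms see promotion messages, so a higher rate is possible. At 15% in both arms, an empty arm occurs in only 1.5% of trials.
- *That all of H3 is affected.* The argument covers starting PrEP. Speaking with a provider may be more frequent; its rate is also unstated.

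The Step 2 figures for equal rates should also not be read as missed effects, because there is no effect to miss. Step 5 is the relevant count there, and it is much smaller. Finally, the remedy below is one of several acceptable choices. Exact logistic regression, or a fallback used only when a cell is empty, would also close the gap.

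**Conclusion.** The point holds for the initiation item, and conditionally. With about 30 men per arm and a true rate of about 5% or less in one arm, that arm is empty in 21% or more of trials. At 10% the problem is small (4%), and at 15% it is negligible. When it happens, the named odds ratio and maximum-likelihood logit model yield no usable effect size. The model's p-value for one table (7/30 v 0/30) can then be 0.999 or 0.001 depending on an unstated choice, against 0.0105 from Fisher's test. The validity of the planned exact test is not in question. The gap is in estimation, and it matters because section 1.5 makes effect sizes the study's main product. The size rests on an assumed initiation rate, which the documents neither state nor rule out.

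**What to change.** In section 6.1, for PrEP initiation:

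1. Keep Fisher's exact test and name it as the test for this item.
2. Make the difference in proportions, with a Newcombe or Miettinen-Nurminen 95% interval, the effect estimate. It stays finite with an empty arm and is a natural planning input for a trial on uptake.
3. For any odds ratio or covariate-adjusted model of this once-measured outcome, replace the maximum-likelihood logit mixed model with Firth-penalised logistic regression and profile-likelihood intervals.

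This needs only wording and standard software, with no new data and no change to conduct. The downside is that the penalised odds ratio is shrunk slightly towards 1. If both arms are empty (0.215² = 4.6% of trials at 5% v 5%), no method gives an informative odds ratio, and the plan should say that only the difference and its interval will then be reported.

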6.2 Data Security

For survey assessments, we will use Qualtrics. Data will be saved to the Qualtrics server, which is encrypted and password protected. All research data will be stored on a password protected OneDrive server and managed by the Rutgers University Information Technology group. Survey responses and neuroimaging data will be kept separately from participants' contact information; the two files will be linked with a non-descript, unique, randomly study ID. Only the PI and a designated senior staff member will have the password to access to the "key" that links the non-descript identifier to personally identifiable information. Written consent forms will be kept in a locked cabinet in a private office with video surveillance.

We will share deidentified data with co-investigators in other institutions or other researchers who express interest in analyzing the data. All data will be stripped of all direct and indirect identifiers and shared via secure server.

After receiving a signed and dated Data Use Agreement and Human Subjects Research Training Certificate from the data requestor, the data custodian will:

- i. seek approval from the Principal Investigator to distribute these data;
- ii. confirm that the data requestor is aware of all applicable data security standards;
- iii. use a method of distribution in accordance with existing policies;
- iv. document the event in an electronic database;
- v. make contact with the data user twice a year to appraise their need to continue using these data;
- vi. electronically retain all communications regarding the continued use of the data.

With the agreement of the PI the data user may continue to use these data. If the user is asked to destroy these data, the user must do so in accordance with the Data Use Agreement policies and must advise the data custodian that these data have been destroyed.

6.3 Data and Safety Monitoring

A. Data/Safety Monitoring Plan

PI will be responsible for implementation and management of the Data/Safety Monitoring Plan (DSMP). Ongoing monitoring will be conducted throughout the study. In addition, Rutgers University IRB will conduct regular reviews of study protocols, changes in study protocols, and adherence to protocols in the field. PI is required to report any unexpected study-related adverse events to the IRB and NIH.

DSMP takes steps to minimize the risk of breach of confidentiality, including procedures to prevent unauthorized use of study data. Names will not be attached to any research instruments or digital files, and all participant data will be identifiable only using the sequentially assigned

Study ID number. All investigators have experience collecting data or conducting interventions with marginalized populations.

Data Gathered During Screening. We will assess potential participants' eligibility for the study using a series of screening questions, which will not include any personal identifying information. We will destroy any and all notes taken during screening after we verify that each participant is eligible for the study.

Study Data. All study data will be password-protected using a password known only to essential project staff. Data will be linked to participants' sequentially assigned Study IDs, but it will not be linked to any personal identifiers. Any identifying information, including the participants' name, email address and phone number, will be kept separate from data at all times. Unique IDs and participant contact details will be stored in a separate database; contact details will be destroyed for each participant immediately after they receive the study compensation. A list of Unique IDs may also be stored on a password-protected file, separate from all study data.

Monitoring. The PI will provide ongoing supervision and training to essential study staff at monthly meetings, which will also ensure continued compliance with data safety protocols. Participants in human subjects research inevitably give up some privacy to share data about their individual experiences; however, we believe our data safety and monitoring plan will minimize the risks of any further breach of privacy or confidentiality. The Investigators will be responsible for ensuring that study protocols for maintaining confidentiality are followed.

Collection, Management and Reporting of AEs and SAEs. Adverse events (AEs) on which reports are collected by the study staff include not only physical harms, such as mortality, suicide, accidents (traffic and other) and violence, but also social harms, such as arrest, incarceration, harassment by the police, being expelled from school or work, and instances of discrimination. Breaches of confidentiality would also be considered an adverse event. Serious adverse events (SAEs) are based on the FDA definition and defined as those that result in death, are life-threatening, result in hospitalization or prolongation of existing hospitalization, a persistent or significant disability, a congenital abnormality or birth defect. Other injuries or medical events may be considered to be serious adverse events when, in the opinion of a physician, they may jeopardize the participant and may require medical or surgical intervention to prevent one of the above outcomes.

In the consent forms, all participants will be reminded to report any physical or social harm to the study staff immediately, so that participants may receive counseling or other assistance. Participants also are asked whether they have suffered any of a list of social harms or other adverse impact that may be attributed to study participation.

When an adverse event is reported to the study staff, the staff investigates the details of the event and reaches a determination as to whether occurrence of the event was related to participation in the study. They will refer the participant to medical, psychological or social services as deemed appropriate, and if deemed necessary by the investigators may take action to terminate the participant from the study.

The staff will complete a "Social Impact Assessment" form which includes:

- A description of the event with probes to identify relationship (specifically a causal relationship) of the event to the participant's involvement in study.
- Coding of the type of event
 - Police/legal problem
 - Housing
 - Employment
 - Health care/insurance
 - Friends/Family
 - Other
- The date at which the event occurred
- If possible, the participant's assessment of the degree to which the event has impacted on his/her quality of life. However, this will not be possible in cases of death, arrest and incarceration in which the participant is unavailable for interview.
- Description of what was done by the study staff and participant to address the event
- Current status of the event and how it was resolved.

AEs and SAEs will be reported to the PI within 24 hours orally or by email and a completed form sent to the PI within 72 hours. A copy of the report will be sent within the NIH project officer and the IRB overseeing the study within one week of completion of the form.

Report of Changes or Amendments to the Protocol. Plans to change or amend the protocols will be reviewed by the Rutgers University IRB. The designated NIH Project Officer will be informed about the approved changes or amendments.

Plans for Interim Analysis of Efficacy data /Trial stopping Rules. Not applicable.

Conflict of Interest. All study investigators are required to complete annually a statement of conflict of interest that is monitored by the IRB.

B. Data/Safety Monitoring Board Details

This is not a phase III clinical trial therefore a DSMB will not be established.

